# 7.2. Participant Discontinuation/Withdrawal from the Study

A participant may withdraw from the study:

- at any time at his/her own request
- at the request of his/her designee (for example, parents or legal guardian)
- at the discretion of the investigator for safety, behavioral, compliance, or administrative reasons
- if enrollment in any other clinical study involving an intervention or enrollment in any other type of medical research judged not to be scientifically or medically compatible with this study, or
- if the participant, for any reason, requires treatment with another therapeutic agent that has been demonstrated to be effective for treatment of the study indication, discontinuation from the study occurs prior to introduction of the new agent.

If a participant is found to be pregnant or breastfeeding during the study, they will be discontinued from the study.

Discontinuation is expected to be uncommon.

At the time of discontinuing from the study, if possible, an early termination visit should be conducted, as shown in the SoA. See SoA (Section 1.3) for data to be collected at the time of study discontinuation and follow-up and for any further evaluations that need to be completed.

If the participant withdraws consent for disclosure of future information, the sponsor may retain and continue to use any data collected before such a withdrawal of consent. If a participant withdraws from the study, they may request destruction of any samples taken and not tested, and the investigator must document this in the site study records.

During the ET visit, the participant will not initiate any new glucose-lowering therapy. Between ET visit and Visit 801, only metformin or insulin can be restarted or increased in dose as needed.

Visit 801 (safety follow-up visit) should be performed approximately 4 weeks after the ET visit as the final study visit.

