# 6.5.4. Management of Gastrointestinal Symptoms

During the double-blind dose escalation period, every effort must be made by the investigator to maintain participants on the dose assigned by IWRS.

This table describes steps the investigator should follow to mitigate GI symptoms and manage participants with intolerable GI AEs during the escalation period.

STEP 1	Advise participants to eat smaller meals, for example, splitting 3 daily meals into 4 or more smaller meals, and to stop eating when they feel full.
STEP 2	Continue STEP 1 +  Prescribe symptomatic medication, for example, anti-emetic or anti-diarrheal medication, per local country availability and individual participant needs. Use of symptomatic medication should be captured as concomitant medication in the eCRF.
STEP 3	Continue STEP 1 + STEP 2 +  Temporarily interrupt tirzepatide; omit 1 dose, the participant will take 3 of 4 doses at that dose level. After the interruption, the investigator should restart the dose or escalate the dose as required, with the participant taking medication to alleviate their GI symptoms. The data related to temporary interruption of study treatment should be documented in source documents.
STEP 4	If intolerable GI symptoms or events persist despite the above measures, the investigator may decide to discontinue study intervention permanently.  Participants who stop study intervention permanently will intensify insulin treatment and/or receive another glucose-lowering intervention (Section 7.1) and will continue participating in the study according to the protocol to collect all planned efficacy and safety measurements. The new glucose-lowering intervention will be recorded on the eCRF for collecting anti-hyperglycemic medications.

Note: De-escalation of study intervention will not be allowed.

Abbreviations: eCRF = electronic case report form; GI = gastrointestinal.

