# **6.8.1.** Rescue Therapy

In any situation that, in the investigator's opinion, may require an intervention that is not consistent with the requirements provided in this section, he or she must also consult the Lilly medical monitor before such intervention is implemented, except when an immediate adjustment of the treatment regimen is medically required.

Insulin therapy and metformin can be used as rescue therapy.

Rescue treatment with GLP-1 RAs or DPP-4 inhibitors are not allowed.

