#### **Definition of rescue therapy**

These definitions assume that a participant has not previously received rescue therapy.

Rescue therapy is defined as any of the following changes in glucose-lowering regimen in response to persistent hyperglycemia:

- A participant treated with metformin + study intervention at baseline receives an increased dose of ≥500 mg metformin and/or insulin at any dose for more than 2 weeks
- A participant treated with metformin + basal insulin + study intervention at baseline receives an increased dose of ≥500 mg metformin and/or any increased dose of >15% basal insulin and/or adding another type of insulin at any dose for more than 2 weeks, or
- A participant treated with basal insulin + study intervention at baseline receives treatment with any increased dose of >15% basal insulin and/or adding another type of insulin at any dose for more than 2 weeks.

If a participant is experiencing severe, persistent hyperglycemia as outlined in section 8.3.3.2, the participant should be considered for rescue. If they are rescued, they will continue in the study and will continue to take study intervention unless the investigator determines that they should not.

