#### **6.8.2.** Allowed Acute Diabetes Therapies

Antihyperglycemic medications other than study interventions are ONLY allowed during these circumstances

- for participants who require permanent discontinuation of study intervention but remain in the study
- for rescue therapy after randomization due to severe, persistent hyperglycemia, or
- during the safety follow-up period.

Short-term insulin use for up to 14 days is allowed for certain clinical situations (for example, elective surgery, during hospitalization, hyperosmolar states) and must be differentiated from insulin use as rescue therapy when reported in the electronic case report form (eCRF).

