# 7.1. Discontinuation of the Study Intervention

In rare instances, it may be necessary for a participant to permanently discontinue study intervention. If study intervention is permanently discontinued, the participant will remain in the study and complete all study visits and procedures as outlined in the SoA (Section 1.3).

This list describes circumstances in which participants will be discontinued from the intervention:

- If participants develop confirmed pancreatitis (if not confirmed, study intervention may be restarted) (see Section 8.3.3.3)
- If a participant is diagnosed with MTC or C-cell hyperplasia after randomization or has calcitonin value ≥35 ng/L that has increased at least 50% over baseline after randomization
- If a participant is diagnosed with an active malignancy or if a previously treated malignancy becomes known after randomization
- If a participant becomes pregnant
- If a participant is diagnosed with T1DM
- Any significant study intervention-related hypersensitivity reaction
- Any other treatment-emergent adverse events (TEAE), SAE, or clinically significant laboratory value for which the investigator believes that permanent study intervention discontinuation is the appropriate measure to be taken, or
- If a participant requests to discontinue intervention.

Participants who stop the study intervention permanently will receive another glucose-lowering medication, if needed per clinical judgment of investigator, and will continue participating in the study according to the protocol to collect all planned efficacy and safety measurements per Section 1.3 (SoA), Section 8.3 (Adverse Events), and Section 8.2 (Safety Assessments) of this protocol. The new glucose-lowering medication will be recorded on the eCRF for antihyperglycemic medications.

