#### 8.3.3.2. Severe, Persistent Hyperglycemia

Severe, persistent hyperglycemia will be collected during the study to assess the risk of extreme imbalance in glycemic control.

Investigators will be trained on the application of criteria for deciding when and how to intervene with participants who do not reach glycemic targets.

Rescue medication as outlined in Section 6.8.1 will be prescribed as an add-on to randomized treatment in the absence of intercurrent cause of the hyperglycemia if the average FBG value of at least 3 values of FBG per week, over 2 consecutive weeks, exceeds these values

- >270 mg/dL (>15.0 mmol/L) from baseline to Week 6
- >240 mg/dL (>13.3 mmol/L) from Week 7 to Week 16, or
- >200 mg/dL (>11.1 mmol/L) from Week 17 to end of study.

Investigators must first confirm that the participant is fully compliant with the assigned therapeutic regimen and that they do not have an acute condition causing severe hyperglycemia.

If applicable, determine if the participant has appropriately titrated the dose for basal insulin prior to deciding if severe, persistent hyperglycemia criteria has been met. Basal insulin should be titrated first before adding any rescue therapy.

Protocol allowed rescue therapies may be added for participants who meet the severe, persistent hyperglycemia criteria, at the discretion of investigator, in accordance with American Diabetes Association/European Association for the Study of Diabetes guidance (ADA 2021c). Rescue medication will be prescribed as add-on to study intervention, and participants will continue to follow the protocol-specified visit schedule.

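### Protocol 7.2 can be read as withdrawing participants before they start another effective agent, while 6.5.4, 6.8.2 and 7.1 keep them in the study

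*Protocol*

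**What the plan says.** Protocol 7.2 lists the grounds on which a participant may leave the study. The lead-in is permissive, but the last bullet states an outcome of its own: if a participant, whatever the reason, "requires treatment with another therapeutic agent that has been demonstrated to be effective for treatment of the study indication, discontinuation from the study occurs" ahead of the new agent. The bullet makes no exception and does not refer to 6.5.4, 6.8.2 or 7.1.

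Those three sections deal with participants who permanently stop study intervention:

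- **6.5.4, Step 4** (persistent gastrointestinal symptoms): "Participants who stop study intervention permanently will intensify insulin treatment and/or receive another glucose-lowering intervention". They then stay in the study so that all planned efficacy and safety measures are collected.
- **6.8.2, first bullet**: antihyperglycemic drugs other than study intervention are permitted "for participants who require permanent discontinuation of study intervention but remain in the study".
- **7.1**: such participants "will receive another glucose-lowering medication, if needed per clinical judgment of investigator, and will continue participating in the study". The opening paragraph of 7.1 also has them complete every visit.

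On the analysis side, the treatment-regimen estimand (SAP 1.1) takes the Week 30 outcome whether or not study intervention was stopped or rescue begun. The FAS (SAP Section 3) keeps the corresponding data, and SAP 4.1.8.1 counts a new antihyperglycemic agent given for more than 2 weeks as rescue. The SAP is not itself inconsistent on this point.

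**The concern.** A participant who stops study intervention and needs another glucose-lowering drug fits both sets of text. One ends study participation before that drug is started; the other has the participant start it and stay. Two sites could handle the same event differently, each able to cite the protocol.

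The statistical stake is Week 30 data in the treatment-regimen analyses, including the primary one. These are the off-treatment outcomes that the estimand sets out to measure. A site that acts on 7.2 before Week 30 turns an obtainable HbA1c into a missing one, and an imputation assumption takes its place. That missingness would come from conflicting wording, not from the participant.

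**Working it through.** **1. The passages side by side**

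| | 7.2, last bullet | 6.5.4 Step 4; 6.8.2 first bullet; 7.1 |
|---|---|---|
| Trigger | Needs another agent effective for the indication, for whatever reason | Has permanently stopped study intervention and needs or receives another glucose-lowering agent |
| Limit on agent | None stated beyond demonstrated effectiveness | None stated |
| Study participation | Ends before the agent is introduced | Continues, with planned measurements |

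The right-hand trigger is a special case of the left-hand one wherever the agent is of proven effectiveness in T2DM. The outcomes are opposite.

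**2. Rescue: a weaker tension**

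Protocol 6.8.1 says of rescued participants, "If they are rescued, they will continue in the study", and 8.3.3.2 says "Rescue medication will be prescribed as add-on to study intervention, and participants will continue to follow the protocol-specified visit schedule". This meets the 7.2 bullet only where rescue adds an agent not used at baseline. Three things limit it: 6.8.1 confines rescue to two drug classes ("Insulin therapy and metformin can be used as rescue therapy"), continued participation is stated expressly, and 7.2 itself treats those two classes separately after early termination ("Between ET visit and Visit 801, only metformin or insulin can be restarted or increased in dose as needed"). Raising the dose of existing metformin or basal insulin is not caught by the bullet.

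**3. What the SAP does with a participant withdrawn under 7.2 before Week 30**

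- The participant has had at least one dose, so remains in the mITT population (SAP Section 3).
- Week 30 HbA1c is missing. In the SAP 4.1.6 table, study discontinuation other than for inadvertent enrollment falls in the row imputed by jump-to-reference at Week 30.
- HbA1c is measured at the early termination visit (Schedule of Activities), but SAP 4.1.6 uses baseline and endpoint values only, so it cannot stand in.
- SAP 4.1.3 excludes anything dated after early termination.
- EAS1 already drops data after study intervention is stopped or rescue begun. For a participant who has stopped study intervention, the efficacy-estimand analysis is therefore the same under either instruction.

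**4. Size**

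The plan's own figure comes first, as background only. Inputs from Protocol 9.5 and SAP Section 5: difference 1.1, SD 1.5, two-sided alpha 0.05, 30 placebo against 60 pooled tirzepatide.

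- SE = 1.5 × √(1/30 + 1/60) = 0.335
- Power = Φ(1.1/0.335 − 1.96) = 0.907; with a noncentral t on 88 df, 0.900

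The stated 90% reproduces. Both documents attach it to an analysis of all data, on or off intervention.

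No rate of exit under the 7.2 bullet is given, so only a count follows. With 90 randomized 1:1:1 there are 30 per arm. Per withdrawn participant:

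- 1/30 = 3.3% of that arm's Week 30 values change from observed to imputed
- 1/90 = 1.1% of all Week 30 values

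Protocol 9.5 randomizes until 90 evaluable participants accrue, a rule SAP Section 5 no longer carries. Under the protocol text the number randomized could exceed 90 and each share would be slightly smaller. The withdrawn participant is still imputed under either text.

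**5. Direction**

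Jump-to-reference gives a withdrawn tirzepatide participant a placebo-like value, and a withdrawn placebo participant one too. Whether that is better or worse than the value follow-up would have recorded depends on the arm and on what the new agent does. No direction of bias and no power loss can be derived from the documents.

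**The case against.** The strongest reply is that the specific rule governs the general one. The 7.2 bullet sits in a list of grounds on which a participant may leave. The sections written for someone who stops study intervention agree with each other. Read together, the bullet would cover only cases outside them, such as a participant still on study intervention who needs an agent the protocol does not permit (6.8.1 bars GLP-1 receptor agonists and DPP-4 inhibitors as rescue). In addition, 6.8.1 sends interventions inconsistent with that section to the medical monitor first, unless an immediate change is medically required. The protocol expects both permanent discontinuation of study intervention and withdrawal from the study to be infrequent. The 1/30 and 1/90 shares are true of any single missing value and say nothing about frequency.

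Much of this stands. The narrower reading is available, the medical-monitor route lowers the chance of a site acting on 7.2 alone, the trigger is probably rare, and one of the two primary analyses is untouched. But the narrower reading is not written into 7.2. The bullet applies whatever the reason, and 7.1 and 6.5.4 do not restrict which glucose-lowering agent they mean. A site would have to infer the limit.

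**Conclusion.** The inconsistency is real and should be fixed. As worded, the last bullet of 7.2 can be read as ending participation for people whom 6.5.4 Step 4, 6.8.2 and 7.1 keep in the study. The rescue sections add only a minor, limited tension.

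The consequence is conditional: it arises only if a site follows the bullet before Week 30, and only in the treatment-regimen analyses. Each such case changes 3.3% of one arm's Week 30 values, or 1.1% of all values, from observed to imputed, assuming 30 per arm. How many cases there would be, and which way they would move the estimate, cannot be told from the documents. In a trial of this size, avoidable missing values on the primary endpoint are worth preventing.

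**What to change.** - Reconcile the last bullet of Protocol 7.2 with 6.5.4 Step 4, 6.8.2 (first bullet) and 7.1, and check the result against 6.8.1 and 8.3.3.2, so that a site meets one instruction on study participation and on Week 30 data collection. Which agents may be used and which clinical rule applies is for the sponsor to settle; nothing is proposed here.
- In the disposition table that SAP 4.2 already plans by arm and reason, identify anyone withdrawn under that bullet. If follow-up is already complete, this still shows whether the conflict touched the data.

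The cost is one wording clarification or site letter and one reason category in an existing table. If the eCRF reason codes do not separate these exits, a small data-collection change or a manual classification would be needed. No extra participants, visits or analyses are required.

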# 7.3. Lost to Follow-up

A participant will be considered lost to follow-up if he or she repeatedly fails to return for scheduled visits and is unable to be contacted by the study site. Site personnel or designee are expected to make diligent attempts to contact participants who fail to return for a scheduled visit or were otherwise unable to be followed up by the site.

# 8. Study Assessments and Procedures

Study procedures and their timing are summarized in the SoA, Section 1.3.

Immediate safety concerns must be discussed with the sponsor immediately upon occurrence or awareness to determine if the participant should continue or discontinue study intervention.

Adherence to the study design requirements, including those specified in the SoA, is essential and required for study conduct.

All screening evaluations must be completed and reviewed to confirm that potential participants meet all eligibility criteria. The investigator will maintain a screening log to record details of all participants screened and to confirm eligibility or record reasons for screening failure, as applicable.

# 8.1. Efficacy Assessments

HbA1c, fasting serum glucose and BMI standard deviation score (SDS) will be used to characterize the efficacy of tirzepatide.

#### **8.1.1.** Patient Reported Outcomes Assessments

The self-reported questionnaires will be translated into the native language of the region and linguistically validated.

The questionnaires should be completed before the participant has discussed their medical condition or progress in the study with the investigator and/or site staff.

The questionnaires should be completed before any other study procedures.

#### 8.1.1.1. **EQ-5D-Y** (Youth)

The youth-friendly EQ-5D-Y version consists of 2 pages, the EQ-5D-Y descriptive system and the EQ visual analogue scale (VAS) (EuroQol Research Foundation, 2020).

Each participant will complete this version of the EQ-5D.

#### The EQ-5D-Y descriptive system

The descriptive system comprises the same 5 dimensions as the EQ-5D 3 level (EQ-5D-3L) but using a youth-friendly wording. The 5 dimensions are

- mobility,
- looking after myself,
- doing usual activities,
- having pain or discomfort, and
- feeling worried, sad or unhappy.

Each dimension has 3 levels: no problems, some problems, or a lot of problems.

The EQ-5D-Y descriptive system will be converted into a single index value by applying a formula that attaches value (also called weights) to each of the levels in each dimension. The index value is a major feature of the EQ-5D instrument, facilitating the calculation of quality-adjusted life years that are used to inform economic evaluations of healthcare interventions.

#### The EQ-5D-Y VAS

The EQ VAS records the respondent's self-rated health on a vertical scale, from, "The best health you can imagine," to, "The worst health you can imagine." This VAS information can be used as a quantitative measure of health outcome as judged by the individual.

#### **Scoring**

Details about scoring are available in the EQ-5D-Y User Guide at EuroQol Research Foundation, EQ-5D-Y User Guide, 2020, available from: https://euroqol.org/publications/user-guides.

# 8.1.1.2. Pediatric Quality of Life Health Inventory (PedsQL)

The PedsQL is a health-related quality-of-life instrument that can be used in healthy children and adolescents and those with acute and chronic health conditions (Varni et al. 2019).

Different versions of the PedsQL (3.2) Diabetes Module and the PedsQL Generic Core Scales are available for children of different ages.

The PedsQL Scoring Manual provides instructions to appropriately score all the dimensions, subscales, and total scores.

#### PedsQL (3.2) Diabetes Module

The PedsQL (3.2) Diabetes Module comprises 33 items for ages 13 years and older, and 32 items (1 less item for the Worry Scale) for ages 2 to 12 years.

This table describes the 5 dimensions of the PedsQL (3.2) Diabetes Module for both age groups.

Dimension	Items per dimension
diabetes symptoms	15
treatment barriers	5
treatment adherence	6
worry	2 (3 for teens and adults)
communication	4

Scores are calculated for each dimension and a total score is available. Higher scores indicate less problems.

#### **PedsQL Generic Core Scales**

The 23-item PedsQL Generic Core Scales were designed to measure the core dimensions of health as delineated by the World Health Organization, as well as role (school) functioning.

This table describes the scales in the generic scale and the summary scores.

Multidimensional Scale	Items per Scale
Physical Functioning	8
Emotional Functioning	5
Social Functioning	5
School Functioning	5
Summary Scores	Items per Summary Score
Psychosocial	15
Physical Health	8
Total	23

Higher scores indicate better health related quality of life.

# 8.2. Safety Assessments

Planned time points for all safety assessments are provided in the SoA, Section 1.3.

#### 8.2.1. Physical Examinations

Height, weight, and waist circumference will be measured and recorded, per Appendix 11, Section 10.11.

Physical exams during in-clinic visits will be performed by a physician.

A complete physical examination at Visits 3, 13, 19, V801 (and ET if applicable) will include, at a minimum, assessments of

- skin
- cardiovascular (CV)
- respiratory
- GI
- neurological systems
- thyroid exam, and
- foot exam including evaluation for diabetic neuropathy.

